7.3.4. Covariates

The study will identify and describe the following variables prior to initiation of *Duavee* or comparator E+P HRT treatment. Applicable operational definitions, including International Classification of Diseases, 9th Revision, Clinical Modification (ICD-9-CM) diagnosis, ICD-9-CM procedure, Current Procedural Terminology (CPT) and Healthcare Common

Procedure Coding System (HCPCS) codes used to identify each variable are shown in Appendix 2.

Patient characteristics:

- Age;
- US region of residence;
- Year of cohort entry (ie, index date); and
- Duration of health plan eligibility prior to cohort entry (in months)

Medical conditions diagnosed during the baseline period:

- Vasomotor symptoms;
- Obesity;
- Osteoporosis;
- Cerebrovascular disease;
- Hyperlipidemia;
- Hypertension;
- Breast pain
- Benign breast lumps (fibrocystic nodule)
- Diabetes;
- Renal disease;
- Osteoarthritis;
- Major depression;
- History of CHD
- History of gallbladder disease;
- History of thyroid disease;
- Family history of cancer;

- At least one diagnosis code indicative of a prior safety event of interest (exclusive of cancers as this is a baseline exclusion criterion).

Use of prescription medications during the baseline period prior to the start of *Duavee* or E+P HRT:

- Corticosteroids;
- Lipid lowering agents;
- Antihypertensives;
- Antidepressants;
- Sedatives/hypnotics;
- Anticonvulsants;
- Antimycobacterials;
- Macrolides;
- Antifungals;
- Antivirals;
- Antidiabetics;
- History of oral contraceptive use;
- History of intrauterine device (IUD) exposure; and
- Unopposed estrogen HRT
- Selective estrogen receptor modulators (SERMs)
- Testosterone
- Local hormone treatments

Additionally, the analyses will describe the most frequently occurring diagnoses and medications seen during the baseline period, the reasons that follow-up was censored and characteristics of medication use during the follow-up period, specifically duration of therapy and time since most recent exposure (measured at the time of censoring from study).

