6.2. Objectives

[figure not shown]
- Primary objective: to estimate the incidence and compare the risks of endometrial hyperplasia and endometrial cancer among postmenopausal women initiating *Duavee* and postmenopausal women initiating E+P HRT during the first four years of *Duavee* availability in the US (2014-2018)
- Secondary objective: to estimate the incidence and compare the risks of selected safety endpoints listed in [Section 7.3.2](#), among postmenopausal women initiating *Duavee* and postmenopausal women initiating E+P HRT.

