7.2. Study Population

Study subjects are all patients identified in the HIRD with minimal exclusion criteria applied. This broad subject eligibility will ensure that the study is representative of the actual ‘real-world’ use of the product in a clinical setting.

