7.2.2. Exclusion Criteria

Patients meeting any of the following criteria will be excluded from the study:

- Patients with an insufficient period of enrollment prior to their index prescription (e.g., 6 or 12 months as determined prior to the start of analysis) will be excluded. This period is necessary to determine if the patient is a new initiator of *Duavee* or E+P HRT without a history of unopposed estrogen use, and also to adequately ascertain baseline covariates/patient history;
- Patients without a uterus, i.e., males, or women for whom evidence of hysterectomy is identified prior to initiation of *Duavee* or comparator E+P HRT; and
- Patients with a history of any type of cancer in their baseline period.
- Patients for whom *Duavee*, comparator E+P HRT or unopposed estrogen are identified during the baseline period will be excluded from the main analyses. They will be evaluated in separate sub-analyses.

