7.4. Time Periods

Each patient will have an index date corresponding to the date of their first prescription for *Duavee* or E+P HRT treatment after 01 May 2014. Baseline characteristics will be assessed from patient data collected prior to their index date (baseline period). A baseline period will be specified in a manner that balances inclusion of as many *Duavee* users as is feasible in the cohort with the need to ascertain covariates prior to the start of treatment. The baseline period will be determined prior to conducting analyses based on review of the distribution of prior continuous health plan enrolment among the *Duavee* cohort of patients.

As described in [Section 7.1](#), follow-up will continue from the first use of *Duavee* or E+P HRT through to the earliest occurrence of a censoring event.

[figure not shown]
Patients will accrue both person-time at risk and person-time on treatment. Analyses will consider patients at risk during the entirety of their follow-up until censoring, regardless of treatment discontinuation. Exploratory analysis will be done on the timing of events in relation to being on treatment.

Scenarios illustrating the duration of the follow-up period are presented in Figure 3.

[figure not shown]
Figure 3. Safety endpoints

- Key:**
- Enrolled in a health plan
 - Exposure to *Duavee*
 - ▨ Exposure to comparator E+P HRT

Patient A: *Duavee* cohort member censored due to use of a comparator E+P HRT

Patient B: E+P HRT cohort member censored due to end of health plan enrolment, history of MI diagnosed at baseline.

Data Source

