7.7.1. Main Analyses

The analyses will describe patients that initiate *Duavee* and the comparator E+P HRT cohort with respect to demographic and clinical characteristics as enumerated in [Section 7.3.4](#). Reasons for censoring will also be described by exposure group. Descriptive comparisons of the two cohorts will be done to document their differences at baseline and to identify potential confounders to be addressed in the propensity matching.

For each of the primary endpoints (i.e., endometrial hyperplasia and endometrial cancer), an IR will be calculated as the number of women meeting a claims-based algorithm for each outcome (first event only) divided by person-time at risk.

The IR and its associated 95% CI will be presented for each cohort overall and stratified by categorical patient age at cohort entry, total duration of *Duavee* or E+P HRT treatment (long vs. short), time since last exposure to *Duavee* or E+P HRT, exposure to local hormone therapy (See Appendix 2), and by presence (Y/N) of an osteoporosis diagnosis within the 90 days before or after initiation of *Duavee* or E+P HRT. Duration of treatment and time since last exposure will be categorized based on observed data distributions. The feasibility of these stratifications and of a possible analysis that stratifies simultaneously by duration of treatment and time since last exposure will be determined based on the number of observed safety events.

Further details of the validation process are described in Appendix 3 and will be contained in the separate Endpoint Algorithm Development Report.

Hazard ratios will be estimated that represent the relative risk associated with initiating *Duavee* as compared to E+P HRT. It is planned to conduct both crude (unadjusted) and adjusted analyses to assess the HR for each of the primary endpoints. Adjusted analyses will use propensity score matching to ensure comparability between treatment groups. Further discussion of the methods to be used in computing propensity scores is included in [Section 7.7.3](#).

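### Women with endometrial hyperplasia already coded at baseline are not removed from the hyperplasia risk set, so follow-up claims for existing disease can count as first events

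*Protocol*

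**What the plan says.** - **Objective (Protocol 6.2).** The primary aim is "to estimate the incidence and compare the risks of endometrial hyperplasia and endometrial cancer".
- **Eligibility (7.2 and 7.2.2).** The population is deliberately broad: "Study subjects are all patients identified in the HIRD with minimal exclusion criteria applied". The exclusions are too little prior enrolment, no uterus, prior study hormones or unopposed estrogen (main analyses only), and one disease history: "Patients with a history of any type of cancer in their baseline period". Hyperplasia is not listed.
- **Covariates (7.3.4).** A prior event of a non-cancer endpoint is a baseline variable: "At least one diagnosis code indicative of a prior safety event of interest (exclusive of cancers as this is a baseline exclusion criterion").
- **Risk period (7.4).** "Analyses will consider patients at risk during the entirety of their follow-up until censoring, regardless of treatment discontinuation".
- **Rate (7.7.1).** The numerator is the women who meet the claims algorithm, "first event only) divided by person-time at risk".
- **Removal after an event (7.1).** An event ends a woman's follow-up for that endpoint only. This is one of the censoring rules for follow-up that begins at first use of the index drug.
- **Algorithm (Appendices 2 and 3).** The hyperplasia algorithm is still to be set through validation. Validation measures the share of flagged women whom record review confirms as true cases.
- **Sensitivity analyses (7.7.4).** The three planned ones cover treatment switch, censoring at cancer, and algorithm misclassification.

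**The concern.** The two primary endpoints are handled differently. Baseline endometrial cancer removes a woman; baseline endometrial hyperplasia does not. For a condition that can be followed over repeated visits and biopsies, a claim after index need not mean disease that began after index. Without an event-free baseline, the first event after index can be the first repeat claim for old disease.

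Existing cases enter the numerators of both cohorts and raise both rates. Because they do not depend on the drug started at index, they add a common amount to each rate and draw a true hazard ratio above 1 towards 1. The protocol wants to say which hazard ratios it can rule out (above 1.39 at year 3 for hyperplasia, Section 7.5), so dilution of this kind favours a reassuring conclusion.

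**Working it through.** **Step 1. Does any rule remove baseline hyperplasia?** Taking the provisions in turn:
- Section 7.2.2 removes cancer history only.
- Section 7.3.4 confirms the split: cancers are left out of the prior-event covariate because they are already excluded, so the other endpoints are in the covariate because they are not.
- The censoring rule in 7.1 acts from index onwards.
- Appendix 2 has comorbidity rows for prior VTE/CVA/CHD and for prior breast, ovarian or endometrial malignancy, but none naming hyperplasia. The covariate is not yet coded for this endpoint.
- The positive predictive value in Appendix 3, and the correction by it in 7.7.4, ask whether the woman is a true case. A woman with known hyperplasia is one, so a high value would not reveal the problem.
- Propensity matching can balance baseline hyperplasia between cohorts but does not take existing cases out of either.

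**Step 2. The plan's own figures (Table 1, hyperplasia, E+P cohort).** Cumulative events are 129 / 274 / 399 and person-years 27,768 / 58,399 / 89,438, giving 4.65 / 4.69 / 4.46 per 1,000 person-years. The stated year-3 interval at a true hazard ratio of 1.0 is (0.72, 1.39). Using exp(±1.96·√(1/d_D + 1/399)) with 9,000 Duavee person-years, d_D = 9,000 × 399/89,438 = 40.2 and the interval is (0.72, 1.38), close to the table. A single 10 months per user (4,500 person-years) gives (0.64, 1.57). How the person-time footnote is to be read is a separate matter and does not affect this point.

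**Step 3. Size under stated assumptions.** The documents give neither the baseline prevalence p nor the share q re-coded after index. Assume p = 0.1% to 0.5% in both cohorts, q = 50% to 100%, and equal follow-up.
- Incident rate r = 399/89,438 = 4.46 per 1,000 person-years.
- Mean follow-up = 89,438/50,350 = 1.78 years.
- Added rate a = p·q/1.78.
- Apparent HR = (HR·r + a)/(r + a).

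| p | q | a per 1,000 PY | existing cases added, E+P (50,350) | added, Duavee (5,400) | true 1.5 reads | true 2.0 reads |
|---|---|---|---|---|---|---|
| 0.1% | 50% | 0.28 | 25 | 3 | 1.47 | 1.94 |
| 0.25% | 50% | 0.70 | 63 | 7 | 1.43 | 1.86 |
| 0.5% | 50% | 1.41 | 126 | 14 | 1.38 | 1.76 |
| 0.5% | 100% | 2.82 | 252 | 27 | 1.31 | 1.61 |

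For the last row: (1.5 × 4.46 + 2.82)/(4.46 + 2.82) = 9.51/7.28 = 1.31. A true hazard ratio of 1.0 stays at 1.0 when prevalence and follow-up are equal.

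This treats the 399 pilot events as all incident. Section 7.5 counts events after the start of E+P use and states no exclusion for prior disease, so some may be existing cases. Replacing r by r − a gives 1.47 in the first row and 1.18 in the last.

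**Step 4. What the pilot suggests.** If re-coding follows soon after entry, the year with most entrants should show an excess. Differencing Table 1:

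| Year | new E+P users | events | person-years | rate per 1,000 PY |
|---|---|---|---|---|
| 1 | 36,651 | 129 | 27,768 | 4.65 |
| 2 | 7,471 | 145 | 30,631 | 4.73 |
| 3 | 6,228 | 125 | 31,039 | 4.03 |

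Entrants fall about five-fold after year 1, yet the rate does not fall in year 2. A Poisson fit with events = λ × person-years + f × entrants puts f, the fraction of entrants re-coded in their entry year, at about 0.03%, with an upper 95% limit of about 0.1%. The assumed p·q runs from 0.05% to 0.5%, so this favours the lower end. At 0.5%, re-coding in the entry year alone would give 0.005 × 36,651 = 183 events, more than the 129 seen.

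**The case against.** **The definition is not final.** The hyperplasia algorithm is open, Appendix 2 lists candidate codes, and a separate algorithm development plan is promised. The language is that of new disease: 7.3.3 speaks of incident events and 7.7.6.3 of first occurrence. A new-onset condition could still be added. This stands as far as it goes: a reader might infer that repeat claims will be counted, and the documents support only that they can be. But eligibility, the covariate role and the risk period are fixed here, and none of them carries out the stated intent.

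**Figure 3.** A reader might take Patient B, "E+P HRT cohort member censored due to end of health plan enrolment, history of MI diagnosed at baseline", as proof that a woman stays at risk for an event she has already had. The caption shows only that she stays in the cohort. Since 7.1 censors by endpoint, she may be followed for the other endpoints.

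**The size is assumed.** This stands. The pilot rates argue against a large share of existing cases, with limits: if half of the re-coding fell in the next calendar year the upper limit for f would be about 0.33%; incidence may rise with exposure; and if the pilot had already excluded prior cases, its rates say nothing about prevalence.

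**Channelling.** If women with known hyperplasia were steered to one product, the crude hazard ratio could move either way. With about 8,700 Duavee person-years (implied by Table 1) and 50% to 100% re-coded, 0.5% prevalence in Duavee against 0.25% in E+P turns a true 1.0 into 1.16 to 1.29; the reverse turns a true 1.5 into 1.27 to 1.13. A reader might carry this over to the main result, but these are unadjusted figures and the propensity score in 7.7.3 targets such imbalance. What matching leaves untouched is the dilution under equal prevalence.

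**Other endpoints.** A reader might extend the point to every non-cancer endpoint. In Appendix 2, VTE, MI and stroke require a hospitalisation, with a principal discharge diagnosis for VTE and TIA and a length-of-stay or death condition for MI and other stroke. A later qualifying admission can be a genuine new event. Renal adenoma is different: two outpatient codes suffice.

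**Conclusion.** The point holds for endometrial hyperplasia and, by the same reasoning, for renal adenoma. As written, baseline hyperplasia does not take a woman out of the hyperplasia risk set, and nothing separates a repeat claim from a new event. This works against the incidence objective and biases a harmful hazard ratio towards 1.

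The direction is firm; the size is not. With equal prevalence of 0.1% to 0.5%, 50% to 100% re-coded and equal follow-up, a true hazard ratio of 1.5 reads about 1.47 to 1.31, and the pilot rates by year suggest the end near 1.47. The documents do not support a claim that the bias is large, that it runs in a particular direction through channelling, or that the hospitalisation-defined endpoints need the same rule. It is worth settling before the first analysis because it decides who counts as a primary event.

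**What to change.** - In 7.2.2 and 7.7.1, restrict the hyperplasia analysis to women with no hyperplasia code in the baseline period, and the renal adenoma analysis to women with no renal adenoma code. Keep these women in the analyses of all other endpoints.
- Add to 7.7.4 a sensitivity analysis that applies the same restriction over all available pre-index HIRD history (the database runs from 2006).
- Leave VTE, MI and stroke as they are.

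**Cost.** One criterion and a filter on data already held. A few women and events are lost. The all-history look-back varies with length of enrolment, so its ability to detect prior disease differs between women; that is why it belongs in a sensitivity analysis and the fixed baseline period in the main one.

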7.3.2. Endpoints

The study will identify non-fatal and fatal events of the following types:

- Primary endpoints:
 - Endometrial cancer;
 - Endometrial hyperplasia.
- Secondary endpoints:
 - Venous thromboembolism;
 - Coronary heart disease (defined as myocardial infarction [MI] and sudden death);
 - Stroke (including transient ischemic attack [TIA]);
 - Breast cancer;

- Ovarian cancer;
- Thyroid cancer;
- Renal cancer and adenoma;
- Gastrointestinal cancer;
- Any cancer (any malignant neoplasm);
- All-cause mortality.

All endpoints are included in the EU risk management plan (RMP) for CE/BZA (*Duavive*). Estrogen-associated cancers (breast, ovarian, endometrial cancers) and endometrial hyperplasia are important potential risks in the RMP based on the medical literature for HRT and background incidence rates (IRs) in postmenopausal women. An important identified risk potentially associated with *Duavee* use is VTE because it is a known safety concern for both of the individual component products of CE/BA (i.e., CE and BZA monotherapies). According to the literature,⁶ MI and stroke are important potential risks that are associated with the use of HRT products in general. Thyroid cancer, renal cancer, renal adenoma, and gastrointestinal tract cancers are considered as important potential risks based on their elevated background incidence in postmenopausal women. All cancers are included because of their inclusion in the EU RMP for CE/BZA. All-cause mortality is included to provide context to fatal occurrences of the safety endpoints. For example, if a finding of increased fatal stroke events is observed, it could be assessed if this result coincided with an increase in all-cause mortality.

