Appendix 2. Codes and Algorithms

Candidate codes and algorithms for identification of exposures, endpoints and covariates are provided below. Final definitions will be determined based on further review of the literature in preparation for development of the first Annual Interim Report, and updates may be provided in the event that additional codes become available during the course of the study (e.g., new GPI, ICD-9-CM, HCPCS or CPT codes become available, including introduction of ICD-10 in the US).

Cohort defining medications

Product	GPI Code
Duavee® (Conjugated estrogens/Bazedoxifene)	24995002100330
Activella® (containing Estradiol, Norethindrone)	2499300212x
Angeliq® (containing Drospirenone, Estradiol)	2499300240x
FemHRT® (containing Ethinyl Estradiol, Norethindrone)	2499300225x
Jinteli™ (containing Ethinyl Estradiol, Norethindrone)	2499300225x
Mimvey™ (containing Estradiol, Norethindrone)	2499300212x
Prefest® (containing Estradiol, Norgestimate)	2499300265x
Premphase® (containing Conjugated Estrogens, Medroxyprogesterone)	2499300204x
Prempro® (containing Conjugated Estrogens, Medroxyprogesterone)	2499300204x

Medications included as covariates

Classification	GPI code
Corticosteroids	22x
Lipid lowering agents	39x
Antihypertensives	36x
Antidepressants	58x
Anticonvulsants	72x
Sedatives/ hypnotics	60x
Antimycobacterial agents	90x

Macrolides	35x
Antifungal	11x
Antivirals	12x
Antidiabetics	27x, excluding 2730x and 2757x
Testosterone	23100030x
Local hormone treatments	2600003010x, 2600004000x, 2600004010x 5535001000x, 5535002000x, 5535002010x, 5535002500x, 5535003000x 5537006000x
History of oral contraceptive use	2510x
	2599x
History of intrauterine devise (IUD)	2505x
	2520x

Comorbidities

Description	Diagnosis and Procedure Codes	
	ICD-9-CM	Procedural
Vasomotor symptoms (VMS)	627.2x, 782.62	
Obesity	278.xx, V77.8x	
Polycystic ovarian syndrome (PCOS)	256.4x, 628.xx, 704.1x,	

CVD (i.e. stroke, transient ischemic attack, sudden cardiac death, myocardial infarction, peripheral vascular disease, coronary artery surgery (CABG), or congestive heart failure)
	
093.0x, 394.xx-397.xx, 398.91, 401.9x, 402.xx, 404.01, 404.03, 404.11, 404.13, 404.91, 404.93, 410.xx-414.xx, 424.xx, 425.4x-425.9x, 427.xx, 428.xx, 429.2x, 429.9x, 433.xx-435.xx, 437.3x, 440.xx, 441.xx, 443.1x-443.9x, 447.1x, 557.1x, 557.9x, 798.2x, 798.9x, V43.4x
	
ICD-9-CM procedure: 36.1x, 36.2x, CPT: 33510-33545 33572

Hyperlipidemia
	
272.0x-272.4x
	

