
Hypertension
	
401.xx-405.xx, 437.2x, V81.1x
	
CPT: 3077F, 3080F

Breast Pain
	
611.71
	

Diabetes
	
250.xx (Type 1: 250.x1, 250.x3; Type 2: 250.x0, 250.x2)
	

Renal Disease	403.01, 403.11, 403.91, 404.02, 404.03, 404.12, 404.13, 404.92, 404.93, 582.xx, 583.0x-583.7x, 585.xx, 586.xx, 588.0x, V42.0x, V45.1x, V56.xx	
Osteoarthritis	715.xx	
Osteoporosis	733.0x, V82.81	
Major Depression	296.2x, 296.3x, 311.xx, V79.0x	HCPCS: G8959, G8960, G8126, G8127, G9193-G9195, CPT: 3088F-3093F
History of VTE/CVA/CHD Event	415.1x, 451.11, 451.19, 451.2x, 451.81, 453.8, 414.xx, 430.xx-438.xx, V12.51-V12.54	
History of Breast, Ovarian, or Endometrial Malignancy	174.xx, 198.81, V10.3x, 198.6x, 183.0x, 236.2x, 182.0x, 198.82, V10.43, V10.42	19120, 58950-58954, 58956-58958, 58960

Family history of cancer	V16.xx	
Hysterectomy	V88.01, V88.02	ICD-9-CM procedure: 68.4x-68.7x CPT: 58150-58294

Potential Algorithms for Claims-Based Identification of Safety Endpoints*

Event	Algorithm
Endometrial Cancer	To be determined via validation
Endometrial Hyperplasia	To be determined via validation
Venous Thromboembolism	Hospitalization with any of the following ICD-9-CM diagnosis codes listed as the principal discharge diagnosis: 415.1x, 451.11, 451.19, 451.2x, 451.81, 453.8x
CHD (i.e. MI, fatal MI, and Sudden Death)	MI defined as a hospitalization with ICD-9-CM code 410.xx (excluding 410.x2) with either (1) a length of stay between 3 and 180 days or (2) discharge status indicating death if length of stay is less than 3 days.
Stroke/TIAs	Hospitalization with ICD-9-CM diagnosis codes 433.x1, 434.x1, 436.x, 437.x1, 437.9x with either (1) a length of stay between 3 and 180 days or (2) death if length of stay is less than 3 days, or hospitalization with a principal discharge diagnosis of 435.xx (TIA)
Breast Cancer	At least two outpatient or one inpatient ICD-9-CM diagnosis code(s) 174.xx.
Ovarian Cancer	At least two outpatient or one inpatient ICD-9-CM diagnosis code(s) 183.0x.

Thyroid Cancer	Thyroidectomy during follow-up and ≥ 2 ICD-9-CM 193.xx diagnosis codes recorded.
Renal Cancer	At least two outpatient or one inpatient ICD-9-CM diagnosis code(s) 189.x
Renal adenoma	At least two outpatient or one inpatient ICD-9-CM diagnosis code(s) 223.x
Gastrointestinal Tract Cancer	At least two outpatient or one inpatient ICD-9-CM diagnosis code(s) 150.x – 159.x

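### Prior VTE has no covariate of its own and no anticoagulant class is listed, so balance on prior VTE is neither ensured nor visible for the VTE comparison

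*Protocol*

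**What the plan says.** The covariate list in Section 7.3.4 of the protocol names "History of CHD" and "Cerebrovascular disease" as conditions in their own right. It does not name prior VTE. A prior VTE is covered only by the last diagnosis item, "At least one diagnosis code indicative of a prior safety event of interest", from which cancers are left out because they are a baseline exclusion.

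In the comorbidity table of Appendix 2, baseline VTE codes occur in one row only, "History of VTE/CVA/CHD Event". Its codes are "415.1x, 451.11, 451.19, 451.2x, 451.81, 453.8, 414.xx, 430.xx-438.xx, V12.51-V12.54".

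The Appendix 2 table "Medications included as covariates" and the matching list in Section 7.3.4 contain antifungals, macrolides and antimycobacterials, but no anticoagulant class.

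The exclusion criteria in Section 7.2.2 do not mention prior VTE. Section 7.3.2 treats VTE as the important identified risk and gives the reason in a sentence that reads in part "use is VTE because it is a known safety concern for both of the individual component products". The other risks named there are called potential. VTE is listed among the secondary endpoints.

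Section 7.7.1 takes the cohort comparison, and from it the confounders for matching, from the characteristics in Section 7.3.4. Section 7.7.3 plans a boosted-regression propensity score and a balance check on the matched groups.

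**The concern.** Two of the three cardiovascular histories have their own line and VTE does not. If the score and the balance table follow the list as written, the two cohorts can agree on the pooled item while differing in how many of the flagged women had a VTE. With no anticoagulant class, no listed drug would reveal the difference. Women with prior VTE stay in the VTE risk set, so such a difference would carry into the VTE hazard ratio.

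Section 7.9 itself warns that prescribing choices may leave one cohort at higher risk for a particular safety event. Clot history is a plausible route for that, although the protocol does not say that it drives the choice between these products. At stake is the adjusted VTE hazard ratio and the reader's ability to judge it.

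**Working it through.** The protocol gives no prevalence of prior VTE, no VTE rate and no VTE precision, so there is no figure of its own to reproduce. The check has two parts.

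**1. Can the other listed items separate prior VTE from the pooled flag?**

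- Non-VTE codes in the pooled row: 414, 430-438 and V12.51-V12.54.
- Appendix 2 has no row named for cerebrovascular disease or for CHD history alone. The nearest is the CVD row, which holds no 415, 451 or 453 code.
- Of the pooled row's non-VTE codes, the CVD row covers 414, 433-435 and, within 437, only 437.3x.
- Not covered: 430, 431, 432, 436, the rest of 437, 438 and V12.51-V12.54.

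A tree-based score that holds both items can form the cell of women with the flag but no CVD code. That cell still mixes VTE with the uncovered codes, and a woman with both a VTE code and a CVD code falls outside it. Prior VTE is isolated only in part.

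**2. How large could the bias be? (illustration, all inputs assumed)**

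Let f be the prevalence of the pooled flag, equal in both cohorts; s0 and s1 the share of flagged women with prior VTE; and RR the risk ratio for a new VTE given a prior one. Then p0 = f × s0, p1 = f × s1, and a true hazard ratio of 1 is multiplied by about

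B = [1 + p1(RR − 1)] / [1 + p0(RR − 1)].

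| Case | f | s0 vs s1 | p0 vs p1 | RR | B |
|---|---|---|---|---|---|
| Moderate, low | 3% | 10% vs 20% | 0.3% vs 0.6% | 3 | 1.012/1.006 = 1.006 |
| Moderate, middle | 6% | 10% vs 20% | 0.6% vs 1.2% | 3 | 1.024/1.012 = 1.012 |
| Moderate, middle | 6% | 10% vs 20% | 0.6% vs 1.2% | 10 | 1.108/1.054 = 1.051 |
| Moderate, high | 10% | 10% vs 20% | 1% vs 2% | 10 | 1.18/1.09 = 1.083 |
| Extreme, low | 3% | 5% vs 40% | 0.15% vs 1.2% | 3 | 1.024/1.003 = 1.021 |
| Extreme, high | 10% | 5% vs 40% | 0.5% vs 4% | 10 | 1.36/1.045 = 1.301 |

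If the excess lies in the other cohort, B is inverted: 1/1.083 = 0.92 and 1/1.301 = 0.77.

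**Visibility.** The standardized difference on prior VTE is (p1 − p0)/√{[p0(1 − p0) + p1(1 − p1)]/2}. It is 0.01/√0.01475 = 0.08 for 1% vs 2%, and 0.035/√0.02169 = 0.24 for 0.5% vs 4%. The pooled flag would show 0 in both cases, so a balance table limited to it could not tell them apart.

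**The case against.** A reader might infer that matching cannot balance prior VTE. The text does not support that. Section 7.7.3 says the score will draw fully on the database's diagnoses, drugs and procedures and does not confine it to the Section 7.3.4 items. It also plans doubly robust estimation. The flag contains the VTE codes, and the separate cardiovascular items isolate them in part, so balance on the flag is not uninformative. Against this, Section 7.7.3 names no variables and Section 7.7.1 points back to the list. Section 7.3.4 promises only to describe other frequent diagnoses and drugs, where an infrequent prior VTE need not appear.

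The link between the Section 7.3.4 item and the Appendix 2 row is itself an inference, since their names differ, and the item could be read as a one-code rule for each event separately. The key to Figure 3 records a baseline MI for one patient, so event-specific history is at least contemplated. The code lists are called candidate. These points stand. They show that the protocol leaves the matter open, not that it settles it, and on either reading prior VTE is not named.

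Two further statements have no support in the documents: that prior VTE is the main predictor of a new VTE, and that chronic heart and cerebrovascular codes will dominate the flag. Neither is relied on here. The general channeling limitation in Section 7.9 already concedes residual confounding, but it speaks of unmeasured or unrecorded factors, whereas prior VTE has codes in Appendix 2.

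**Conclusion.** The point holds in limited form. Prior VTE has no covariate of its own, the one Appendix 2 row that codes it is pooled, and no anticoagulant class is listed. Following the list as written, balance on prior VTE is neither ensured nor shown for the one endpoint called an important identified risk. It does not follow that the VTE hazard ratio will be confounded.

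The size is unknown. The factors of about 1.01 to 1.08 (moderate) and up to 1.30 (extreme) rest on an assumed flag prevalence of 3-10%, assumed VTE shares, assumed risk ratios of 3 to 10, and no help from any other covariate. The upper end needs a 5% vs 40% split inside a perfectly balanced flag. VTE is secondary, and the primary endometrial hazard ratios are untouched. This is a low-cost improvement, not a flaw that undermines the study.

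**What to change.** - Split the combined Appendix 2 row into three covariates: prior VTE, prior stroke/TIA and prior CHD. Assign each of V12.51-V12.54 to the covariate it belongs to.
- Name prior VTE in Section 7.3.4.
- Add baseline anticoagulant dispensing to the medication lists in Section 7.3.4 and Appendix 2.
- State in Section 7.7.3 that these covariates enter the propensity model, and report balance on each after matching.
- Optionally, add as a sensitivity analysis a VTE hazard ratio restricted to women with no baseline VTE code and no baseline anticoagulant dispensing.

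The first four changes are edits to lists and text and use medical and pharmacy claims already in the database. The optional analysis costs one more estimate and loses a few events.
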